### **Subject Recruitment and Compensation**

Describe recruitment procedures, including who will introduce the study to potential subjects. Describe
how you will ensure that subject selection is equitable and all relevant demographic groups have access
to study participation (per 45 CFR 46.111(a) (3)). Include information about approximately how many
DUHS subjects will be recruited. If subjects are to be compensated, provide specific prorated amounts
to be provided for expenses such as travel and/or lost wages, and/or for inducement to participate.

Subject Recruitment and Compensation. Focus group and user testing participants will be 40 patients who have undergone HCT and have reported pain, fatigue, and distress post-transplant in addition to 6 healthcare professionals (e.g., nurses, oncologists) who provide care to HCT patients. RCT participants will be 40 patients. The amount of time patients are h ospitalized for their HCT varies based on the type of transplant they receive (e.g., autologous vs. allogeneic). Thus, patients who undergo an autologous transplant will be approached either pre- or post-transplant. Pre-transplant approach and consent will happen 1 week to 1 month before a scheduled transplant and post-transplant approach and consent will happen up to 3-months post-transplant. Patients who undergo an allogeneic transplant will be approached within 1-month post-transplant.

Drs. [name] (PI) and [name] (Co-I) will work closely with the study oncology physician champion ([name] [Co-I]) to facilitate recruitment of patient participants in their clinics. Drs. [name] and [name] (Co-I) have worked with the ABMT providers on past trials and successfully recruited cancer patients with pain, fatigue, and distress.

Patient participants will be recruited under a Waiver of Consent and HIPAA authorization. [name] and his team will provide the study team with the names and medical record number of all participants scheduled for transplant. Then, the study team will gather information from medical records to assess whether or not the patient meets study inclusion criteria (i.e., cancer diagnosis) and is at least 18 years old. The study team will also collect medical information related to transplant type and date to use to appropriately time recruitment. Other information gathered at this time will include cancer type, date of diagnosis, recurrence date, patient date of birth, sex, marital status, education, race, cancer stage, and height/weight. Once a potential study participant has been identified and they are within the study recruitment window, study staff will mail the patient a letter signed by the study PI and oncology physician champion ([name]) informing them of the study and providing contact information to decline/opt out. We will attempt to meet potential participants at the transplant clinic to attempt recruitment, or by phone if we are unable to meet them in clinic (e.g., due to time constraints). For patients approached by phone (e. g., due to time constraints in clinic), we will wait 3 days from mailing the study letter to allow time for the patient to receive the letter. When contacting by phone, the study team member will follow the IRB approved script to introduce and explain the study, describe study procedures, and assess the patient's interest and eligibility. If the patient is interested and eligible, the study team member will schedule a time to meet the patient in clinic or in the study team's research office to obtain written consent (Pain Prevention and Treatment Research Program, [name]). For those approached in clinic, a member of the medical team known to the patient will first ask the patient's permission to have a member of the study team approach them. We will not be using cold-contact. Once permission is given, a member of the study team will approach the patient and describe the study procedures. If the patient remains interested, they will

complete the written consent process prior to their participation in the study. A member of the study team will answer any questions that the potential participant may have. Once informed consent has been received, participants will be scheduled for a study appointment either to happen at that time or a time convenient for them in the future. A member of the study team will conduct the appointment. If a participant declines study participation at any point during these procedures, the information provided to the study team through the medical team or medical records will be immediately de-identified. At this first study appointment, the study team member will explain all study procedures and administer the baseline assessment.

Compensation. User testing and RCT participants will receive \$20 for completing each of the two study assessments (pre-treatment and post-treatment; total \$40). All participants will continue to receive standard medical care from their medical team. No participant will be asked to change or decline any strategies for symptom management based on their participation in this study.

\*Due to COVID-19, we propose a temporary amendment. This temporary amendment suspends in-clinic approaches. Study staff will continue to mail out a letter, no cold-contact, and then will approach by telephone. Compensation procedures will remain the same.

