Randomized Controlled Trial. We will use a small RCT to assess the feasibility, acceptability, and outcome patterns suggesting efficacy of a HCT Coping Skills Training for Symptom Management and Daily Steps (HCT Symptoms and Steps) protocol. This study will be conducted in the ABMT Clinic with 40 HCT patients. Following consent (consent process detailed below), participants will be randomly assigned in equal allocation to one of two conditions: 1) HCT Symptoms and Steps or 2) HCT Education. HCT Symptoms and Steps will provide patients with cognitive behavioral coping skills training and activity coaching sessions to enhance their ability to manage symptoms that interfere with activity. All participants will receive a wireless activity tracker (Fitbit) to track steps; Fitbits will not be returned, participants will keep their Fitbit. All participants who do not have a smart phone will be lent one (iPhone) equipped with Internet access to access the mHealth features: video-conferencing, coping skill content, activity tracker syncing, daily symptoms assessment, and personalized feedback (via push notification) based on symptom and step data. HCT Education will only have access to activity tracker syncing and daily symptoms assessment. HCT education participants will be encouraged to download the Transplant (HCT) Guidelines mobile app that is free of charge. The Transplant Guidelines app is developed by the National Marrow Donor Program and designed for HCT patients with a focus on treatment guidelines for patients before and after transplant. The Transplant Guidelines App provides recommended annual check-up guidelines and timing and contains helpful information, checklists and reminders for patients who have had a blood or marrow transplant. App content also includes cancer education, information about health and well-being, cancer treatment guidelines specific to HCT patients, and what to expect at follow-up visits. App features allow participants to use a GvHD symptom checker to help identify early signs of GvHD and make notes, e-mail guidelines and symptom checker results to self, and set reminders for appointments, medications, and exercise. All participants will complete 2 assessments: pretreatment and post-treatment. We will recruit 10 patients per quarter (3-4/month) to complete the recruitment goal of 40. Participants will receive \$20 for completing each assessment. Th erapist Training. Coping skills training sessions will be delivered by a doctoral level psychologist with experience delivering cognitive behavioral interventions. Activity coaching sessions will be delivered by an OT with expertise working with HCT patients. Treatment strategies will be taught through didactic instruction, audio-/video-recorded illustration of techniques, and role-play. Procedures to Ensure Consistency of Treatment. To ensure consistency with the intervention protocol: 1) therapists will follow a treatment manual, 2) weekly supervision will occur, 3) sessions will be audio-recorded and reviewed during supervision and feedback provided, and 4) ratings of treatment adherence and competence will be conducted.

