Aim 3 Analyses. Between-group effect sizes will be used to evaluate treatment effects on physical disability, as well as pain, fatigue, psychological distress, physical activity, and self-efficacy for symptom management. Between-group effect sizes will provide an index of relative change for HCT Symptoms and Steps participants vs. HCT Education participants. Because small samples can differ on pretest scores, effect sizes will be calculated by first creating change scores for each person. The between-group effect size will then be calculated by subtracting the average HCT Education group change score from the average HCT Symptoms and Steps change score, and dividing this difference by the standard deviation of the pooled treatment/control group's change score. This study is not designed to make conclusions about efficacy without further study.

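### Baseline is not anchored to transplant, and neither the stated randomisation nor the Aim 3 effect sizes account for transplant type or timing, which costs some precision and dilutes the standardised effect

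*Combined protocol and SAP*

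**What the plan says.** Subject Recruitment and Compensation sets three entry routes. Autologous patients may enter by either of two: "Pre-transplant approach and consent will happen 1 week to 1 month before a scheduled transplant", or "post-transplant approach and consent will happen up to 3-months post-transplant". For the third, "Patients who undergo an allogeneic transplant will be approached within 1-month post-transplant".

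These windows date approach and consent. The link to baseline comes later in the same section: after consent, "participants will be scheduled for a study appointment either to happen at that time or a time convenient for them in the future", and "At this first study appointment, the study team member will explain all study procedures and administer the baseline assessment". Nothing ties that appointment to the transplant date.

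The Randomized Controlled Trial paragraph says that "This study will be conducted in the ABMT Clinic with 40 HCT patients" and that "participants will be randomly assigned in equal allocation to one of two conditions". It gives no stratification factor, blocking or minimisation. It plans two assessments, before and after treatment.

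Under Aim 3 Analyses, "effect sizes will be calculated by first creating change scores for each person". The difference in mean change is then divided by the pooled SD of change, with no covariates. Transplant type and date are already collected before enrolment, but the only use stated is to time recruitment.

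**The concern.** A change score measured from a pre-transplant baseline spans the transplant itself. One measured from a baseline 3 months after transplant does not. The planned effect size averages both as if they were the same quantity.

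The plan uses change scores because small groups can differ at pretest. That deals with a difference in baseline level. It does not deal with a difference in natural course between recovery phases, which goes straight into the change score.

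Two things follow if the phases do differ. The pooled SD of change is larger, so the standardised effect is smaller. And with 20 patients per arm, the arms may by chance hold different shares of each phase. The Aim 3 effect sizes matter beyond this pilot because the background says that its results will be used to prepare an efficacy trial.

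**Working it through.** **The plan's own figure.** N = 40 rests on precedent (earlier pilots of 15 to 40), with no alpha, power, effect size or SD, so no formula reproduces it. Only the accrual arithmetic can be checked: 10 per quarter × 4 = 40, which agrees.

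**Spread of baseline.** By the consent windows alone, baseline may lie from about 1 month before to 3 months after transplant, about 4 months in all. It may be later still, since the appointment may follow consent.

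**Inputs**
- From the documents: 40 patients, equal allocation, hence 20 per arm; unadjusted change scores divided by the pooled SD of change.
- Assumed, because the documents do not give them: K, the number of the 40 in one of two classes (pre- or post-transplant baseline, or transplant type), taken as 4 to 20, with q = K/40; and D, the gap in mean change between classes in within-class SDs, taken as 0.5 to 1.5. A true d of 0.50 on the within-class scale is used as an illustration.

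**Step 1: chance imbalance.** Without stratification, the number k of class members in one arm is hypergeometric (40, K, 20). The arms differ by |2k − K| patients.

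| K of 40 | P(differ by 4 or more) |
|---|---|
| 4 | 11% |
| 8 | 24% |
| 12 | 30% |
| 16 | 33% |
| 20 | 34% |

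**Step 2: effect on d.** Mixing classes multiplies the SD of change by t = √(1 + q(1 − q)D²).
- A 4-patient difference shifts d by (4/20) × D / t.
- A true d of 0.50 reads 0.50 / t.
- The effective sample size is 40 / t².

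At q = 0.5 and D = 1, t = √1.25 = 1.118. The shift is 0.20/1.118 = 0.18, 0.50 reads 0.45, and 40/1.25 = 32. At q = 0.1 and D = 1, t = √1.09 = 1.044. The shift is 0.19, 0.50 reads 0.48, and 40/1.09 = 36.7.

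| Gap D | Shift in d from a 4-patient difference | True 0.50 reads | 40 patients are worth about |
|---|---|---|---|
| 0.5 SD | 0.10 | 0.49 | 38–39 |
| 1.0 SD | 0.18–0.19 | 0.45–0.48 | 32–37 |
| 1.5 SD | 0.24–0.27 | 0.40–0.46 | 26–33 |

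Ranges run over K = 4 to 20.

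**Step 3: comparison with ordinary sampling error.** The SE of d with 20 per arm is √(2/20) = 0.316. The imbalance is part of this figure. At q = 0.5 and D = 1 its SD is 0.143, and removing it leaves √(0.316² − 0.143²) = 0.283. The shift and the lost information in the table are therefore two views of one variance and must not be added.

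**The case against.** The other side has a good case, and much of it stands.

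- *Bias.* A reader might infer that the Aim 3 comparison is biased. It is not. Randomisation makes the phases equal in expectation, and the imbalance component sits inside an SE of about 0.32 that sampling gives anyway.
- *Baseline date.* A reader might infer that every patient consented before transplant has a pre-transplant baseline. The documents do not say so. The appointment may be later, the assessment is called pretreatment, and the background describes an intervention that starts straight after transplant. A pre-transplant baseline is permitted, not required, and how many patients would have one is unknown.
- *Stratification.* Its absence is inferred from silence; the protocol gives no randomisation method at all and does not rule it out.
- *Size.* Neither K nor D is in the documents. They contain no outcome trajectories, and the background stresses persistent symptoms. At D = 0.5 the effect is negligible.
- *Purpose.* Aim 3 is exploratory, the plan itself disclaims efficacy conclusions, and wide entry windows suit a pilot that needs 40 patients in 12 months. The Aim 2 benchmarks are untouched.

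What remains is that no text anchors baseline, stratifies or adjusts, although the data needed to adjust are already collected.

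**Conclusion.** The point holds as a low-severity improvement in precision. The documents let baseline fall on either side of transplant and state neither stratification nor adjustment, so the Aim 3 effect sizes may mix recovery phases. The cost is added variance and a diluted standardised effect.

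The size depends on the assumed class share and gap. It is trivial at a gap of 0.5 SD. It becomes material at 1 SD or more if a sizeable share of patients is in each class: at 1 SD and an even split, about a fifth of the information is lost (40 down to 32). A gap that large is plausible where the change score spans the transplant, but the documents neither show nor exclude it. They do not support the stronger statement that imbalance is likely to create or conceal an effect: even at a 1 SD gap, the imbalance component of d has an SD of 0.09 to 0.14 over K = 4 to 20, against a total SE of 0.32.

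**What to change.** 1. **Aim 3 Analyses.** Estimate the between-group effects with a model that includes transplant type and baseline timing relative to transplant (before/after, or days from transplant), and report them with confidence intervals. State which SD standardises the result: dividing by the unadjusted pooled SD of change would leave the dilution in place. The data are already collected. Cost: one or two degrees of freedom at N = 40.
2. **Randomized Controlled Trial paragraph.** Stratify randomisation in small permuted blocks by one two-level factor, transplant type (autologous or allogeneic). Cost: a stratified allocation list. This alone leaves autologous baselines spread over time, so the timing covariate is still needed.
3. **Optional, Subject Recruitment and Compensation.** For patients consented before transplant, take the baseline after transplant and before randomisation. This is debatable. Aim 2 Analyses counts attrition over all who consented, so losses between consent and randomisation would count against that benchmark unless its denominator is restated.

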#### **Consent Process**

• Complete the consent section in the iRIS Submission Form.

### **Subject's Capacity to Give Legally Effective Consent**

• If subjects who do not have the capacity to give legally effective consent are included, describe how diminished capacity will be assessed. Will a periodic reassessment occur? If so, when? Will the subject be consented if the decisional capacity improves?

Not applicable.

### **Study Interventions**

• If not already presented in #4 above, describe study-related treatment or use of an investigational drug or biologic (with dosages), or device, or use of another form of intervention (i.e., either physical procedures or manipulation of the subject or the subject's environment) for research purposes.

Study interventions presented in #4 above.

#### **Risk/Benefit Assessment**

• Include a thorough description of how risks and discomforts will be minimized (per 45 CFR 46.111(a) (1 and 2)). Consider physical, psychological, legal, economic and social risks as applicable. If vulnerable populations are to be included (such as children, pregnant women, prisoners or cognitively impaired adults), what special precautions will be used to minimize risks to these subjects? Also identify what available alternatives the person has if he/she chooses not to participate in the study. Describe the possible benefits to the subject. What is the importance of the knowledge expected to result from the research?

### **Risk/Benefit Assessment**

Potential Risks. The primary risks of this study are those associated with confidentiality. There is some risk attendant to confidentiality of self-report data. Two password-protected databases will be used for this study to ensure confidentiality. First, a tracking database will be used for recruitment and follow-up. This data will house information related to tracking the participants in the study, such as phone numbers and addresses. No medically sensitive or outcome data will be stored in this database. This database will also track nonparticipants (i.e., those who have declined participation) only to the barest minimum to ensure that they are not contacted again about participation. At the end of the study, all identifiable data of non-participants such as their names will be deleted. Tracking data on participants will be retained for the usual required period. Second, all study data will be stored in a separate password protected REDCap database without any personal identifiers. Data in this database will be derived from patients' direct input into REDCap, which is an online survey system; data entered into this system is stored on a secure server housed behind the Duke University Medical Center (DUMC) firewall. Only a unique study identification number will link the electronic data to the study data file. The tracking data and study data will be stored in a file on a secure DUMC psychiatry server which can only be accessed by necessary members of the research team. Access to the Duke network requires a password protected, 128-bit encrypted virtual private network connection provided by Cisco systems.

There are few risks linked to participating in in-clinic activity coaching sessions with an occupational therapist that center on daily steps. The activity coaching component of the intervention is being designed in part by hematology oncology providers and an occupational therapist who specializes in working with hematology oncology patients. Further, the activity coaching sessions will be led by a senior level occupational therapist at Duke University Hospital who holds a lymphedema therapist certification and specializes in working with hematopoietic stem cell transplant (HCT) patients pre- and post-transplant. The activity coaching component of the intervention is consistent with clinical recommendations for activity post-transplant and will be modified based on the patient participant's level of functioning. We will obtain physician clearance for activity prior to initiating the intervention sessions. While we do not anticipate any adverse events, we have developed a protocol to protect against and track adverse events related to exercise injuries /falls, lymphedema flares, hypotension or hypoglycemia, and cardiovascular events.

The risks associated with this study are minimal and rare. During the assessments, participants will be asked to complete a walking test. The 6 minute walk test will be conducted in a hallway at the Duke ABMT Clinic or in a hallway in our research lab office space at the Pain Prevention and Treatment Research Program located in Erwin Square ([name]). Study staff (e.g., CRC, Occupational Therapist) will complete the 6 minute walk test. The 6 minute walk test is optional for participants; if a patient declines, we will not conduct the test. Further, we will check patients' blood pressure prior to conducting the 6 minute walk test and if any of the following contraindications are present, we will not conduct the test: (1) unstable angina during the previous month, (2) myocardial infarction during the previous month, (3) resting heart rate >120, (4) systolic blood pressure >180 mm Hg, (5) Diastolic blood pressure >100 mm Hg. There are some risks associated with the 6 minute walk test. During the 6 minute walk test, a participant may experience difficulty with breathing, shortness of breath, chest pains, dizziness, and/or light headedness. There is also the potential risk of a fall during the 6 minute walk. The study investigators, including the medical oncologist co-investigator, and the study team will take all precautions possible to avoid and minimize these risks (e.g., checking blood pressure and other contraindications prior to conducting test, making test optional). Should any of these occur, appropriate emergency care (e.g., 911) will be provided. A defibrillator is

available at the ABMT Clinic, and so are nursing and other medically trained staff. Over the course of the intervention, participants will be asked to participate in in-person/in-clinic activity coaching sessions led by a certified, senior level occupational therapist and to continue this activity and skills practice on their own at home. While we do not anticipate any adverse events and the intervention is consistent with physical activity recommendations, participants may be at risk for adverse events related to physical activity such as injuries/falls, lymphedema flares, hypotension or hypoglycemia, and cardiovascular events. Again, we will obtain physician clearance for activity prior to initiating the intervention sessions and should any of these adverse events occur, appropriate emergency care (e.g., 911) will be provided. Overall, the benefits of the intervention outweigh the risks and the activity coaching component is consistent with recommendations from HCT oncology providers, occupational therapists specializing in HCT care, and national guidelines for HCT patients.

Potential Benefits and Importance of Information to be Gained. This study has several potential benefits. First, hematopoietic stem cell transplant patients with pain, fatigue, and psychological distress who participate in the intervention may learn ways to enhance their symptom coping strategies and increase their physical activity. Intervention participants may experience significant decreases in symptom severity and physical disability as well as increases in physical and psychological functioning. Second, if the proposed HCT Symptoms and Steps protocol proves to be feasible, acceptable, and shows promise for efficacy, it could be applicable to a number of patient populations with a similarly high symptom burden who face challenges similar to hematopoietic stem cell transplant patients with pain, fatigue, and distress. Third, the proposed model of intervention delivery has the potential to be expanded to intervene on a number of other needs faced by patients with chronic illness (e.g., medication adherence, caregiver burden). The proposed intervention model has the potential to dramatically redesign existing modes of behavioral intervention delivery, improve continuity and coordination of care, and improve patient outcomes.

